11.1 Evaluation and Reporting of Adverse Events

All AEs (i.e., a new event or an exacerbation of a pre-existing condition) that occur from the time informed consent is signed and up to 30 days after the study drug has been discontinued must be recorded as an AE on the AE eCRF. The Investigator must follow all AEs until the AE resolves, or until the Investigator and/or the Medical Monitor determine the event is chronic or clinically stable. If an AE remains unresolved at the conclusion of the study, the Investigator and Medical Monitor will make a clinical assessment to determine whether continued follow-up of the AE is warranted. All participants who have received at least one exposure to study therapy will be evaluated for safety of study treatment.

The Investigator should attempt to establish a diagnosis of the event based on signs, symptoms and/or other clinical information. In such cases, the diagnosis should be documented as the AE and not the individual signs/symptoms.

11.2 Assessment of Adverse Events

All AEs must be promptly documented on the Adverse Event eCRF and assessed by the Investigator. Details of the event must include the dates of onset and resolution, severity,

relationship to study drug, seriousness, and whether the event caused the participant to withdraw from the study, outcome and timing with regard to administration of the study drug.

Severity: Severity should be graded and recorded according to the table below.

Severity	Definition	
Mild	Awareness of event but easily tolerated	
Moderate	Discomfort enough to cause interference with usual activity	
Severe	Inability to carry out usual activity, incapacitating, requires medical intervention	

Relationship: The relationship of the Adverse Event to the study drug will be determined by the Principal Investigator, and assessed using the following definitions:

Relatedness	Description
Not Related	There is no evidence of a causal relationship and a causal relationship cannot be reasonably attributed to the study treatment or procedures. The event is clearly due to extraneous causes.
Unlikely Related	A poor temporal relationship exists between the event onset and administration of intervention. The event could easily be explained by the participant's clinical state, intercurrent illness, or concomitant therapies.
Possibly Related	A relationship cannot be ruled out with certainty and the event may be related. There is some evidence to suggest a causal relationship but the influence of other factors may have contributed to the event, such as the participant's clinical condition or concomitant treatment.
Probably Related	The event is likely related to the intervention. There is evidence to suggest a causal relationship, such as reasonable temporal sequence from treatment administration or procedure. The influence of other factors is unlikely.
Definitely Related	The event is clearly related to the intervention. There is clear evidence to suggest a causal relationship. The influence of other factors can be ruled out.

These criteria, in addition to good clinical judgment, should be used as a guide for determining the causal assessment. If it is felt that the event is not related to study drug therapy, then an alternative explanation should be provided.

11.3 Collection and Reporting of Serious Adverse Events

Following written consent to participate in the study, all SAEs, whether related or not related to study drug, must be collected, including those thought to be associated with protocol-specific procedures. The reporting period ends 30 days after discontinuation of dosing. In addition, the investigator should report any SAE occurring after this time period that is believed to be related to study drug or protocol-specific procedures. Serious adverse events that occur prior to initiation of study drug will be documented in the EDC as medical history, but will still need to be reported to on an SAE form as described below.

An SAE is an AE from this study that results in any of the following outcomes:

- Death
- Life-threatening situation (participant is at immediate risk of death)
- Inpatient hospitalization or prolongation of existing hospitalization
- Persistent or significant disability/incapacity
- Congenital anomaly/birth defect in the offspring of a participant who received study drug

Considered significant by the investigator for any other reason

An SAE report should be completed for any event where doubt exists regarding its status of seriousness.

If the investigator believes that an SAE is not related to the study drug, but is potentially related to the conditions of the study (such as a withdrawal of previous therapy or a complication related to study procedure), the relationship should be specified in the narrative section of the SAE Report Form.

SAEs, whether related or not related to study drug, overdose, and potential drug induced liver injury must be reported within 24 hours of the Investigator becoming aware of the event. For this study we will be capturing SAEs through both the ADCS Electronic Data Capture (EDC) system and on an SAE report form provided by CCI In addition, all applicable SAEs must be reported by the Site Investigator to the Institutional Review Board (IRB) of record according to IRB's reporting requirements for such events.

The Site Investigator is responsible for reporting all SAEs and all Other Important Medical Events to via telephone, immediately or no later than 24 hours after awareness of the event. A representative will then immediately notify the Biohaven Medical Monitor. An SAE form must then be submitted to via the fax number indicated below.

Safety Hotline Number for SAE telephone reports:

North America: PPD

Facsimile (fax) number for SAE report forms, to be sent within 24 hours after awareness of the event:

North America: PPD

The Site Investigator, or designated staff, is also responsible for entering the SAE information in the ADCS Electronic Data Capture (EDC) system (i.e., event term, start stop dates, causality, and severity) according to study-specific eCRF Completion Guidelines. The ADCS Medical Monitor and ADCS Project Director will be automatically notified via email upon entry of an SAE into the ADCS EDC system. A member of the ADCS Medical Safety team will inform the DSMB of the occurrence of any SAEs within 7 days of being reported. The DSMB may at any time request additional information from the ADCS in relation to a reported event.

If only limited information is initially available, follow-up reports are required. If an ongoing SAE changes in its intensity or relationship to study drug or if new information becomes available, a follow-up SAE report should be sent to within 24 hours of the Investigator becoming aware of the updated information using the same procedure used for the transmission of the initial SAE and the same event term should be used. In addition, new or revised event information must be entered into the ADCS EDC at the same time.

All SAEs should be followed to resolution or stabilization. For any questions relating to SAEs, please contact the ADCS Medical Monitor via telephone or email at the number listed on the protocol face page.

Suspected Unexpected Serious Adverse Reactions

Suspected unexpected serious adverse reactions (SUSARs) are serious adverse events that are not listed in the Investigator's Brochure as an expected AE and that the Investigator assesses as possibly related or probably related or definitely related to study drug or study procedure. United States 21 CFR 312.32 and European Union Clinical Trial Directive 2001/20/EC and the associated detailed guidance or national regulatory requirements in participating countries require the reporting of SUSARs to regulatory authorities. As the clinical trial sponsor, Biohaven is responsible for, and has procedures consistent with regulations that will be followed for, expedited reporting of SUSARs.

11.4 Overdose Reporting Requirements

For the purposes of this study, an overdose is the accidental or intentional administration of any dose of study drug greater than the highest daily dose (either 140 or 280 mg as prescribed per protocol) within a calendar day. Any overdose must be reported on the eCRF. An overdose is not an AE unless it results in untoward effects. Any AEs related to the overdose must be reported on the AE and/or SAE page of the eCRF. No specific antidote for the overdose of BHV-4157 is known. Signs and symptoms of overdose should be treated according to standard of care.

11.5 Clinical Laboratory Abnormalities and Other Abnormal Assessments

[figure not shown]
Laboratory abnormalities are usually not recorded as AEs unless considered to be clinically significant by the site clinician. An abnormal laboratory result will be considered an AE if it is associated with clinical signs or symptoms, if the abnormality is of a degree that requires active management (e.g., discontinuation of the study drug, dose modification) or when the event is requiring treatment or other therapeutic intervention (e.g., iron supplements, blood transfusion, etc.).

The Investigator will evaluate the relationship of any significantly abnormal result to protocol treatment and clinical condition, if possible. All clinically significant abnormal laboratory results will be followed until they return to normal or become stabilized.

11.6 Pregnancy and Breast Feeding

BHV-4157 should not be used during pregnancy or while breast-feeding. The lower age limit for this study is 50 years, and women must be post-menopausal for at least 2 consecutive years or surgically sterile (bilateral tubal ligation, hysterectomy or bilateral oophorectomy) for at least 6 months prior to screening to be eligible for this study.

12 STATISTICAL METHODS

As the interim analysis will not stop the study for success, we have not adjusted the final analysis and have maintained the alpha at 5% in order to avoid inflating the

probability of a type 1 error. Complete details of the interim, efficacy, and safety analyses are provided in a separate Statistical Analysis Plan (SAP), which is maintained by ADCS in consultation with Biohaven.

12.1 Sample Size and Power Determination

12.1.1 Overall Study Power

Using approximately 336 randomized participants (with a 1:1 assignment 168 per arm), this study has at least 80% power to reject the null hypothesis of no efficacy in favor of the alternative that BHV-4157 is efficacious, given the assumption of a difference in the mean change from baseline to 12 months between the BHV-4157 arm and placebo arm of 2.64 points on the ADAS-Cog 11, and 0.95 points in CDR-Sum of Boxes, and under a range of effect sizes which give 93.7% probability of proceeding at the interim analysis.

This calculation assumes no more than a 26% dropout rate, which would leave 336 X 0.74 = 248 participants available at the final analysis, or 124 per arm. The calculation also assumes a standard deviation of 6 points on the change in ADAS-Cog 11 in each arm at both 6 months and 12 months, and a standard deviation of 2.3 points on the change in CDR Sum of Boxes at 12 months; in addition, a correlation of 45% between 12 month change on the co-primary ADAS-Cog 11 and CDR Sum of Boxes endpoints are assumed. These assumptions are supported by published retrospective data from historical ADCS studies (Thomas, Albert, Peterson, & Aisen, 2016). The computations use a 2-sided 2-sample t-test at 5% alpha to approximate power.

Briefly, the statistical reasoning is as follows:

- P(pass overall) = P(pass final | pass interim)P(pass interim) ≥ P(pass final) P(pass interim)
- P(pass final) = P(pass final ADAS) P(pass final CDR | pass final ADAS)
- 3. Numerical integration shows that P(pass final CDR | pass ADAS) is about 3% greater than P(pass final CDR), given the assumed 45% correlation between these endpoints.

Hence, if P(pass interim) = 0.937, P(pass final ADAS) = 0.92, and P(pass final CDR) = 0.90, then P(pass overall) \geq 0.92 x (1.03 x 0.90) x 0.937 = 0.80.

With 124 subjects per arm, the unconditional power for the ADAS-COG endpoint is 92%, if the mean difference in change is 2.64 points with standard deviation of 6 points within each arm. At this sample size, the unconditional power for the CDR-SOB endpoint is 90%, if the mean difference is 0.95 points with standard deviation of 2.3 points within each arm. Hence, if the interim analysis has power 0.937 or greater to pass, the overall power is 80% or more following the statistical reasoning given above.

For perspective, we note that the assumed difference of 2.64 points on ADAS-Cog is 68% of the decline observed in the placebo arm of 3.9 points in studies of mild to moderate AD from (Thomas,

Albert, Petersen, & Aisen, 2016). The assumed difference of 0.95 points on CDR-SOB is 59% of the decline observed in the placebo arm of 1.6 points (Thomas, Albert, Petersen, & Aisen, 2016).

12.2 Analysis Populations

Analysis populations are defined as follows:

- Enrolled Participants: Participants who signed an informed consent form and were assigned a Participant Identification number (PID).
- Randomized Participants: Enrolled participants who received a treatment assignment. This
 group forms the ITT population.
- Treated Participants: Enrolled and randomized participants who received at least 1 dose of blinded study therapy (BHV-4157 or placebo). This will be the primary analysis population used for safety summaries.
- The modified Intent-to-Treat (mITT) population will include all randomized participants who took at least one dose of the study medication, who have a baseline assessment of

the co-primary efficacy endpoints, and who have at least one efficacy evaluation following baseline. This will be the primary analysis population used for the efficacy analyses.

- Open-Label Extension Treated Participants: Participants enrolled in the extension phase who received at least 1 dose of open-label extension phase study therapy (BHV-4157). This will be used for safety summaries of the extension phase
- The modified Intent-to-Treat (mITT) population for the Extension Phase will include all Open-Label Extension phase participants who took at least one dose of Extension phase study medication, who have at least one efficacy evaluation during the extension phase. This will be the analysis population used for the efficacy summaries for the extension phase
- All BHV-4157 Treated Participants: Participants enrolled who received at least 1 dose of BHV-4157 in either Randomization or Extension Phase of the study. This will be used for safety summaries of the extension phase

The primary population for all efficacy analyses in the double-blind treatment phase is the mITT population, without imputation for missing values. A sensitivity uses the mITT population with multiple imputation. The Treated Participants will be used for analyses of safety endpoints.

12.3 Analysis of the Co-Primary Endpoints

The primary study hypothesis is that treatment with BHV-4157 will result in a reduction in total within-participant change from baseline on the ADAS-Cog 11 score and also on the CDR Sum of Boxes, relative to the placebo group at week 48 of the double-blind treatment phase in the mITT population. The co-primary endpoints at the final analysis will be tested using a hierarchical gatekeeper strategy: if ADAS-Cog 11 is significant at the 5% level, then CDR-SOB will also be tested at 5% significance level. If ADAS-cog is not significant at the 5% level, then CDR-SOB will not be included in the primary analysis, and will be presented for descriptive purposes only. The primary objective of the trial is met only when both coprimary endpoints are significant.

The primary analysis for each outcome uses a mixed effects repeated measures model, including all available in-clinic outcomes during the double-blind phase in the mITT population. Fixed effects in the model are APOE status (e4 carrier vs e4 noncarrier), MMSE (mild vs moderate) status, site, baseline score (ADAS-cog or CDR-SOB), treatment group (active vs placebo), visit, visit x baseline score, and visit x treatment group interaction. Visit is treated as a categorical variable. Sites with only one subject will be pooled.

A random effect will be included for participant. The within subject covariance will be unstructured. If the model fails to converge, MMSE status will be removed from the model. If the model still does not converge, the following covariance structures will be fit, sequentially, until the structure is found that results in convergence of the model: Huynh-Feldt, Toeplitz, Autoregressive (1), and Compound Symmetry. Error degrees of freedom will be calculated using Kenward-Roger approximation if an unstructured covariance structure fits appropriately; otherwise, a sandwich estimator will be utilized to estimate the covariance structure and degrees of freedom will be calculated using the between-within method (Schluter & Elashoff, 1990).

Each co-primary endpoint is tested using model-adjusted least squares means at the week 48 visit of the double-blind treatment phase. Point estimates, standard errors, 95% confidence intervals, and p-values will be presented.

Further details of the primary analysis, including sensitivity analysis and methods for handling missing data, are presented in the statistical analysis plan.

12.4 Analysis of Secondary Endpoints

If both the co-primary endpoints are significant, mean changes in the secondary endpoints from baseline to week 48 of the double-blind treatment phase are compared using the analysis strategy outlined above, or if appropriate, a two-sided, two-sample t-test. For these secondary endpoints, a Holm step-down test is conducted at 5% level to control the familywise error rate. These endpoints are: bilateral hippocampal volume as measured by volumetric MRI; NPI total scores; ADCS-ADL; and MMSE scores.

If the co-primary endpoints fail to both reach significance, then the secondary endpoints, will be analyzed as exploratory using the same strategy outlined above.

Categorical variables are summarized by treatment group using frequency distribution: number of non-missing observations and percentages will be given. Continuous variables are summarized using standard quantitative statistics: number of non-missing observations, mean, standard deviation, median and range (minimum and maximum observed values).

12.5 Analysis of Exploratory Endpoints

The exploratory endpoints include: (1) change in MoCA scores from baseline to week 48; (2) change in ADCOMS total score from baseline to week 48; (3) bilateral lateral ventricles and whole brain volume as measured by volumetric MRI; (4) a cognitive composite outcome computed using measures from the NACC Neuropsychological Test Battery (Craft Story 21 Recall (Immediate & Delayed), Benson Figure (Copy & Delayed Recall), Multilingual Naming Test (MINT), Letter & Category Fluency, Trail Making Test A & B, Number Span Forward & Backward; (5) BHV-4157 pharmacokinetics; (6) treatment response by Apo E genotype; and (7) CSF, serum and plasma biomarker panel (AB42, AB42/40 ratio, total tau, p-tau-181, neurogranin, NfL, YKL-40, VILIP, SNAP-25, sTREM2, GFAP) at week 24 and week 48. CSF will be assessed in a subset of the study population (estimated n=50 active, n=50 placebo). Their analyses are included in the SAP.

12.7 Open-Label Extension Phase Analysis

Any analyses of efficacy endpoints from the extension phase will be exploratory only.

12.7.1 Efficacy Analysis

Efficacy endpoints will be summarized with descriptive statistics for the Open-Label Extension Phase by treatment group and week. For the extension phase, subjects will be summarized by the original randomized treatment group and will reflect 1) continued BHV-41257 treatment and 2) Placebo subjects switched to open-label BHV-4157. Additional exploratory endpoint of evaluating long-term effects on clinical outcome measures

12.7.2 Safety Analysis

Safety endpoints include adverse events, physical exam, vital signs, health status, 12 lead ECG, laboratory determinations and participant withdrawals. Safety and tolerability data as well as demographic data will be summarized in tabular and/or graphical format for each treatment group. The incidence of all laboratory test abnormalities and the median changes from baseline will be tabulated by treatment regimen and time point. The safety population will be used for these analyses.

Safety will be presented separately for the double-blind phase and for the open-label extension phase, overall and by randomized arm.

12.7.3 Adverse Events

Treatment emergent adverse events (AE) occurring, or intensifying, after the start of study drug dosing a r e summarized descriptively for the safety population. A listing is prepared of Serious Adverse Events occurring in subjects that are enrolled but not treated. All AEs are coded

according to system organ class (SOC) and preferred term (PT) using the Medical Dictionary for Regulatory Activities (MedDRA). Summary tables showing the number of participants and percent of unique subjects within each category are generated for each of the following types of adverse events and its relationship to study treatment (related to study treatment):

- All events
- Serious events
- Deaths
- Events leading to discontinuation of treatment
- Severe events
- Events occurring with a frequency of more than 5% in either treatment group

12.7.4 Laboratory Parameters

Laboratory parameters are summarized by visit. Frequencies of high and low values with respect to the normal range are displayed, as are shift tables comparing each treatment visit (weeks 4, 8, 12, 24, 36, and 48) and baseline visit by time point and treatment group.

12.7.5 Other Safety Parameters

Vital signs and ECG parameters are summarized across groups by visit using descriptive statistics, and at each outcome visit and at end of study.

Physical examination findings and number of participants are summarized as the count and percentage of participants by eCRF pre-defined categories at last visit. Concomitant medications are summarized by treatment group, drug class and preferred term. Vital signs are summarized by visit using descriptive statistics.

Overall interpretation results for ECGs and the Investigator interpretation results are collected as normal, abnormal not clinically significant, and abnormal clinically significant. Participants whose interpretation shifts from normal to abnormal are listed separately including description of the abnormality and any associated comments.

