- 8. Brain MRI at screening shows evidence of infection, tumor, cortical infarction, extensive white matter disease (Fazekas score > 2), or multiple lacunes in prefrontal or critical memory regions; inconclusive findings may be subject to review by the ADCS Imaging Core.
- History of a major depressive episode within the past 6 months of screening.
- History of schizophrenia diagnosis.
- History of bipolar disorder.
- History of seizures within 2 years of screening.
- History of alcohol abuse or dependence or drug abuse in the past 5 years.
- Insulin-dependent diabetes or uncontrolled diabetes with HbA1c value >8.0 %.
- Hepatitis B, C, or HIV infection.
- Clinically significant laboratory abnormalities that may influence study assessments as determined by the investigator.
- Untreated or insufficiently treated hypothyroidism, vitamin B12 or folate deficiency.
- 18. ECG obtained during screening that, in the opinion of the investigator, is clinically significant with regard to the participant's participation in the study. Corrected QT interval (QTcF) must be evaluated using Fridericia's formula, and must not exceed 480 msec.
- 19. Cancer or a malignant tumor within the past 3 years, except patients who underwent potentially curative therapy with no evidence of recurrence for >3 years. Patients with stable prostate cancer or non-melanoma skin cancers are not excluded.

- 20. Participation in another clinical trial for an investigational agent and having taken at least one dose of study medication, unless confirmed as having been on placebo, within 12 weeks prior to screening. The end of a previous investigational trial is defined as the date of the last dose of an investigational agent.
- Having received riluzole for more than 4 weeks prior to screening or with known tolerability difficulties to riluzole.

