8.6 Electrocardiogram

A standard 12-lead resting ECG will be performed during screening, week 12, week 24, and week 48 of the Open-Label Extension phase. The Investigator or designee will review the 12-lead ECG and findings will be recorded in the eCRF as normal, abnormal but not clinically significant, or abnormal and clinically significant. Any clinically significant abnormalities on ECGs recorded after administration of the investigational product will also be documented as AEs and entered on the AE page of the eCRF. Clinically significant abnormalities on ECGs prior to administration of the investigational product, will be recorded as medical history.

8.7 vMRI Assessments

Brain structural change is seen in normal aging, but is accelerated in neurodegenerative disease, including AD. Atrophy in AD arises from neuron and synapse loss that begins in the entorhinal cortex. The pathology then spreads throughout the limbic regions of the temporal lobe, including the hippocampal formation. Subsequently, neuron loss and atrophy is observed throughout neocortical association areas in temporal, parietal and frontal lobes.

vMRI allows the *in vivo* assessment of brain structure volume and provides a measure of atrophy rate. Results from vMRI studies suggest that the patterns of atrophy in AD, which mirror the pathological progression of the disease, can reliably be detected and tracked across time. Atrophy of the medial temporal lobe, including hippocampus and entorhinal cortex, has long been described in vMRI studies of AD. Hippocampal volume derived from MRI correlates with histological hippocampal volume and degree of neuronal loss and AD pathology, and entorhinal cortical thickness change appears to be an early and sensitive indicator of neurodegeneration associated with AD (Holland et al., 2009; Jack et al., 2004). Longitudinal MRI measures of regional and whole-brain volumetric change provide a valuable complement to cognitive measures in that they are not influenced by temporary symptomatic improvements, and they provide an early index of the study drug's ability to reach the target organ and have an effect on AD-related atrophy.

Participants will undergo vMRI scans of the brain at screening, week 24 and week 48 (and Extension Phase baseline and week 48) in order to assess for changes in brain volumes that may be associated with clinical change due to treatment with BHV-4157.

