11 DEFINITION OF ADVERSE EVENTS

An adverse event (AE) or adverse experience is any untoward medical occurrence in a study participant who is administered a medicinal product, that does not necessarily have a causal relationship with the study treatment, and that occurs after informed consent is signed and up to 30 days after the study drug has been discontinued. An AE can therefore be any unfavorable and unintended sign, symptom, or disease temporally associated with the use of a medicinal product, whether or not considered related to the medicinal product. Pre-existing conditions, which increase in frequency or severity or worsen in nature during, or as a consequence of, use of a drug in human clinical trials, will also be considered adverse experiences. Adverse events may also include pre- or post- treatment complications that occur as a result of protocol-mandated procedures (e.g. invasive procedures such as biopsies).

An AE does not include:

- Medical or surgical procedures (e.g., surgery, endoscopy, tooth extraction, transfusion).
 The condition that leads to the procedure is the AE.
- Situations where an untoward medical occurrence has not occurred (e.g., hospitalization for elective surgery, social and/or convenience admissions).
- Worsening of symptoms associated with expected decline in Alzheimer's disease is not considered an adverse event in this study.
- Overdose of either study drug or concomitant medication without any signs or symptoms unless the participant is hospitalized for observation. Overdoses should be reported as outlined in Section 11.4.

A treatment emergent adverse event (TEAE) is defined as any AE that developed, worsened, or became serious after first dose of study drug and prior to 30 days after the last dose of study drug.

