#### 4.10.6 Electrocardiogram

Descriptive statistics for ECG interval data (e.g., QRS, PR, QT, QTcF), and ventricular heart rate will also be reported by visit for the Randomization and Extension Phases, separately. The summary will be based on the data after the date/time of first dose of study drug and within 30 days after the last dose of study drug (see section 4.3 for detailed definition of "on-treatment").

In addition, the number and percentages of subjects with at least one post-treatment QTcF > 450 ms, >480 ms, and >500 ms will be summarized for the Randomization and Extension Phase, separately, as well as the overall BHV-4157 treated exposure. Similar number and percentages will be presented for subjects with at least one post-baseline QTcF Change from baseline >= 30 ms to < 60ms and those with at least one change from baseline >= 60 ms. A subject listing will provide each QTcF sign measure, specifying any subject meeting the criteria with a complete list of their QTcF assessments with the ones meeting the criteria indicated.

The criteria summarized for the Randomization Phase will also be repeated for Treated subjects completing (or discontinuing) double-blind treatment prior to versus on or after start of COVID-19 pandemic crisis (March 13, 2020).

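### The protocol's ECG interpretation listing omits worsening from abnormal-not-clinically-significant to clinically significant, and no planned output shows within-participant worsening by arm (minor)

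*Protocol*

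**What the plan says.** Protocol 8.6 has the investigator or designee review each 12-lead ECG, and "findings will be recorded in the eCRF as normal, abnormal but not clinically significant, or abnormal and clinically significant". Protocol 12.7.5 repeats the three levels ("collected as normal, abnormal not clinically significant, and abnormal clinically significant") and gives one explicit output for them: "Participants whose interpretation shifts from normal to abnormal are listed separately including description of the abnormality".

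On entry, exclusion criterion 18 in Protocol 7.2 concerns an "ECG obtained during screening that, in the opinion of the investigator, is clinically significant" with regard to participation, and adds a QTcF limit of 480 msec. It does not remove an abnormal ECG judged not clinically significant.

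After dosing, Protocol 8.6 adds: "Any clinically significant abnormalities on ECGs recorded after administration of the investigational product will also be documented as AEs". Section 11 also counts as adverse experiences "Pre-existing conditions, which increase in frequency or severity or worsen in nature during, or as a consequence of, use of a drug".

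Protocol section 12 refers to the SAP for the complete safety analysis. SAP 4.10.6 states: "Descriptive statistics for ECG interval data (e.g., QRS, PR, QT, QTcF), and ventricular heart rate will also be reported by visit". It then adds counts above QTcF thresholds of 450, 480 and 500 ms, counts of QTcF change from baseline (30 to under 60 ms, and 60 ms or more), and a QTcF listing that marks participants meeting the criteria. It does not mention the interpretation category.

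**The concern.** A listing of ECG deterioration should include every kind of deterioration the scale can record. This one takes its starting point as normal, so a participant whose baseline ECG is NCS cannot meet the rule, even if a later ECG is judged CS. A participant who moves from normal to NCS, a milder end state, does meet it.

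ECGs are a stated safety measure, and Protocol 4.2.2 says they will be assessed for differences between the groups. A participant listing is not a between-group comparison, and the SAP's ECG section provides none for interpretation. Laboratory data are treated more fully: Protocol 12.7.4 plans shift tables by treatment group, and SAP 4.10.3 plans shifts from baseline to the worst on-treatment value. At stake is the completeness of one safety display and the agreement of the two documents on whether it will be produced.

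**Working it through.** The plan gives no figure on this point, so the check is an enumeration set against the text.

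**Possible worsening shifts.** Three ordered categories give 3 × 2 / 2 = 3 worsening pairs.

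| Worsening shift | Protocol 12.7.5 listing | Named in SAP 4.10.6 | Must be recorded as an AE (Protocol 8.6) |
|---|---|---|---|
| Normal to NCS | Yes | No | Not by this rule |
| Normal to CS | Yes | No | Yes |
| NCS to CS | **No** | No | Yes |
| Covered | 2 of 3 | 0 of 3 | 2 of 3 |

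**Can the omitted row occur?** Yes. Criterion 18 turns on clinical significance and QTcF, so an NCS screening ECG is compatible with enrollment. The visit schedule has no ECG at the baseline visit, so under the SAP Table 3 note (last assessment on or before the first day of study drug) the scheduled double-blind baseline ECG is the screening one.

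**What do the other outputs show for that row?**
- *Adverse events.* An NCS-to-CS change is recorded under 8.6. SAP 4.10.2 treats events that first occur or worsen after first dose as treatment-emergent, counts them by treatment group and phase, and lists all AEs. These tables are organized by system organ class and preferred term. They show neither the baseline ECG category nor how many participants in each category were available to worsen.
- *Intervals and QTcF.* These are reported whatever the baseline interpretation. They need not reflect a change of rhythm or morphology.
- *General rule in SAP 4.10.* Categorical safety variables are summarized by number and percentage per category for each arm, with visit-level denominators. Applied to interpretation, this would give counts of normal, NCS and CS by visit.

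**Would by-visit counts replace a shift table?** No, because they lose the pairing. As an invented illustration, take two participants, one normal and one NCS at baseline, and a later visit with one NCS and one CS. Those counts fit normal to NCS plus NCS to CS (two participants worsen). They fit equally well normal to CS with the other unchanged (one worsens). Under 12.7.5 each case lists one participant.

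**Which baseline should apply in each phase?** SAP Table 3 uses the last assessment on or before the first day of randomization-phase drug. SAP Table 5 uses the last on or before the first day of extension drug, provided it is within 28 days. The screening ECG is therefore not the right reference for the extension.

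**The case against.** The strongest reply is that the serious shift is already captured, and by arm. Any CS finding after dosing goes to the AE page regardless of the baseline reading, worsening of a pre-existing condition counts, and treatment-emergent events are tabulated by treatment group. That stands. A reader might infer from 12.7.5 that participants who go from NCS to CS disappear from the report; the documents do not support that.

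Three other stronger readings also fail:
- *That normal-to-abnormal shifts are the whole ECG output.* SAP 4.10.6 plans interval, heart-rate and QTcF outputs that do not depend on baseline interpretation.
- *That the 12.7.5 listing is the only planned output on interpretation.* The general rule in SAP 4.10 names ECGs among the safety measures and arguably covers the three-level variable. Protocol 12.7.2 likewise asks for safety data in tables or graphs by treatment group. Silence in the ECG subsection does not establish absence from the plan.
- *That the listing catches only trivial changes.* Abnormal includes both abnormal categories, so normal to CS is listed.

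What the reply leaves standing is narrow. The listing rule, as worded, leaves out one of the three worsening shifts. The SAP's ECG section does not reproduce the listing, and neither the AE tables nor by-visit counts show the within-participant change by arm. The AE route also depends on a separate site entry, which an interpretation table drawn from the ECG page could be used to check.

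**Conclusion.** The point holds as a minor reporting gap and a free improvement. The listing covers 2 of 3 worsening shifts, SAP 4.10.6 names 0 of 3, and no specified output shows worsening of interpretation from baseline by arm. This rests on reading the 12.7.5 rule literally and on NCS ECGs being admissible under criterion 18.

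The number affected cannot be sized. The documents give no rate of NCS ECGs at entry and no rate of later worsening. A reader might assume a baseline rate and multiply by the 336 planned participants, but that would count everyone who starts as NCS rather than those who worsen, and each who reaches CS should have an AE record. Co-primary and secondary efficacy analyses, power and error control are unaffected, and so is the required capture of clinically significant ECG events.

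**What to change.** 1. In Protocol 12.7.5, reword the listing to cover participants whose interpretation worsens by at least one category from the phase-specific baseline, meaning the last ECG on or before first dose of that phase, as in SAP Tables 3 and 5 (with Table 5's 28-day limit for the extension). Carry the same wording into SAP 4.10.6.
2. Add to SAP 4.10.6 a shift table of baseline category against worst on-treatment category, by arm, for each phase. Use the on-treatment periods in SAP 4.4 and take the worst over all ECGs in the period, since the SAP's visit-window rule keeps only the latest record per window. Show participants without a baseline or on-treatment ECG as missing. For the extension, use the original randomized groups.

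The cost is one sentence and one table. The interpretation is already recorded in the eCRF, so no new data, visits or participants are needed, and sample size and alpha do not change.
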